Please indicate which s	tatements best describe your own health state today.
Mobility	I have no problems in walking about I have some problems in walking about I am confined to bed
Self- Care	I have no problems with self- care I have some problems washing or dressing myself I am unable to wash or dress myself
Usual Activities	I have no problems with performing my usual activities

E.g. \	Work, study, house	I have some problems with performing my usual activities I am unable to perform my usual activities ework, leisure or family activities
Pain/	/Discomfort	I have no pain or discomfort I have moderate pain or discomfort I have extreme pain or discomfort
Anxie	ety/Depression	I am not anxious or depressed I am moderately anxious or depressed I am extremely anxious or depressed
In yo	ur own opinion, h	ow good or bad is your own health today on a scale of 0-100 (Where 100 is the best imaginable health state and 1 is the worst)
For N	Mothers only - Att	achment Questionnaire
1.	When I am carin	g for the baby, I get the feeling of annoyance or irritation Very frequently Frequently Occasionally Very rarely Rarely
2.	When I am caring trying to upset mentions to upset mentions and the caring to upset mentions are upset mentions.	g for the baby I get the feeling that the child is deliberately being difficult or ne Very frequently Frequently Occasionally Very rarely Rarely
3.	Over the last two	No strong feelings towards the baby Slight affection Moderate affection
	•	Intense affection

4.	Regarding my overall level of interaction with the baby, I: • Feel very guilty that I am not more involved
	Feel moderately guilty that I am not more involved
	Feel slightly guilty that I am not more involved
	I don't have any guilty feelings regarding this
5.	When I interact with the baby I feel: • Very incompetent and lacking in confidence
	Moderately incompetent and lacking in confidence
	Moderately confident and competent
	Very confident and competent
6.	When I am with the baby I feel tense and anxious: • Very frequently
	Frequently
	Occasionally almost never
7.	When I am with the baby and other people are present I feel proud of the baby: • Very frequently • Frequently • Occasionally • Almost never
8.	I try to involve myself in as much as possible PLAYING with the baby: • This is true • This is untrue
9.	When I have to leave the baby: • I usually feel rather sad (or it's difficult to leave) • I often feel rather sad (or it's rather difficult to leave)
	I have mixed feelings of both sadness and relief
	I often feel rather relieved (and it is easy to leave)
	I usually feel rather relieved (and it is easy to leave)
10.	When I am with the baby: • I always get a lot of enjoyment /satisfaction

 I frequently get a lot of enjoyment /satisfaction
I occasionally get a lot of enjoyment/satisfaction
I rarely get a lot of enjoyment/satisfaction
When I am not with the baby, I find myself thinking about the baby: • Almost all the time • Very frequently • Frequently • Occasionally • Never
When I am with the baby: • I usually try to prolong the time I spend with him/her • I usually try to shorten the time I spend with him/her
When I have been away from the baby for a while and I am about to be with him/her again, I usually feel: Intense pleasure at the idea Moderate pleasure at the idea Mild pleasure at the idea No feelings at all about the idea Negative feelings about the idea
I now think of the baby as: • Very much my own baby • A bit like my own baby • Not yet really my own baby
Regarding the things that I/we have had to give up because of this baby: I find that I resent it quite a lot I find that I resent it a moderate amount I find that I resent it a bit I don't resent it at all

16.	Over the past 3 months, I have felt that I do not have enough time for myself: • Almost all the time
	Frequently
	A few times
	Not at all
17.	Taking care of this baby is a heavy burden of responsibility. I believe this is: • Very much so
	Somewhat so
	Slightly so
	Not at all
18.	I trust my own judgement in deciding what my baby needs: • Very much so
	Somewhat so
	Slightly so
	Not at all
19.	Usually when I am with the baby: I am very impatient I am a bit impatient I am moderately patient I am extremely patient
Instru	others only – Edinburugh PND score ctions: Please tick one option for each question that is closest to how you have felt for the SEVEN DAYS
1.	I have been able to laugh and see the funny side of things • As much as I always could
	Not quite as much now
	Definitely not so much now
	Not at all
2.	I have looked forward with enjoyment to things

	As much as I ever did	
	Rather less than I used to	
	Definitely less than I used to	
	Hardly at all	
3.	I have blamed myself unnecessarily when things went wrong • Yes, most of the time	
	Yes, some of the time	
	Not very often	
	No, never	
4.	I have been anxious or worried for no good reason	
	No, not at all	
	Hardly ever	
	Yes, sometimes	
	Yes, very often	
5.	I have felt scared or panicky for no very good reason • Yes, quite a lot	
	Yes, sometimes	
	No, not much	
	No, not at all	
6.	Things have been getting on top of me	
	Yes, most of the time I haven't been able to cope at all	
	 Yes, sometimes I haven't been coping as well as usual 	
	 No, most of the time I have coped quite well 	
	No, I have been coping as well as ever	
7.	I have been so unhappy that I have had difficulty sleeping • Yes, most of the time	
	Yes, sometimes	
	Not very often	
	No, not at all	

8.	I have fe	It sad or miserable: Yes, most of the time	[
	•	Yes, quite often						
	•	Only occasionally						
	•	No, never	Ī					
		,	_					
9.	I have be	en so unhappy that I ha Yes, most of the time	ve been (crying				
	•	Yes, quite often	Ī					
	•	Only occasionally	Ī					
	•	No, never	Ī					
			L					
10.	The thou	ght of harming myself h Yes, quite often	as occurr [IB if you hav	ve any tho	oughts of harming	
	•	Sometimes			your	self, plea	se tell us today	
	•	Hardly ever						
	•	Never						
_	SMART – onment	18 month questionnair	e					
Have	you move	ed house since your last	visit?					
	Yes							
	No							
		nswer the following: or town do you live?						
In wh	at type of	area do you live?	Urban		Rura	al	population<2000)
If you	live in a r	ural area, do you live on	ı a:	Farm Open cou	-			

How many people live in your house?			
Number of Adults			
Number of children			
Do you work in paid employment at the moment	:? Yes	No	
If Yes, how old was your baby when you returned	d to work?		
Age in months			
If your child attends childcare please fill out the child does not attend any childcare, please tick d		ding all forms of c	hildcare. If your
Type of childcare	How many hours spent per week in childcare	How many other children minded	
Child minder			
Nursery/Creche			
Minded by family member (e.g. grandparent)			
Minded in own home by child minder or au pair			
Minded in own home by family member			
Does not attend (minded by mum and dad)			
Have your smoking habits changed since your las	st visit?		
No			
If Yes, please answer the following:			
Do you currently smoke? Yes	No Yes	s e-cigarettes onl	у
If Yes, how often do you smoke?			

Daily	How many a day
2/3 times a week	
Once a week	
Less than once a week	
Do you allow smoking in you	ur house?
No	
Yes, occasionally	
Yes, daily	
Yes, e-cigarettes only	
Is your baby exposed to smo	oking outside the home (eg. grandparents?)
No	
Yes, occasionally	
Yes, daily	
Yes, e-cigarettes only	
How often do you bath you	r baby?
Once a week	
2-3 times a week	
3-5 times a week	
Daily	
Other, please specify	
What do you use in the bath Please specify product name	
How often do you moisturis	e your baby's skin?

Never
Once a week
2-3 times a week
Daily
Several times a day
Occasionally
What do you use to moisturise your baby's skin? Please specify product name and brand
Feeding
Does your child still take a bottle?
Yes
No
If Yes, how many bottles a day do they take of the following
Infant formula
Growing up milk
Cow's milk
• Other
If other please specify
Does your baby use a soother/dummy?
Yes, regularly
Yes, occasionally
No L
Sleeping
Sleeping Arrangements
Infant cot in separate room

Infant cot in parent's room
In parent's bed
Infant cot in room with sibling
Other, please specify
Sleeping Position
On his / her belly
On his / her side
On his / her back
Sleeping time during the day (between 7am and 7pm) Hours
Sleeping time during the night (between 7pm and 7am) Hours
How long does it take to put your baby to sleep in the evening? Hours Minutes
Wakefulness time between 10pm and 6am Hours
How does your baby fall asleep?
While feeding
Being rocked
Being held
In bed alone
In bed near parent
When does your baby usually fall asleep at night (24 hour format)?
Time

Do you consider your baby's sleep a problem?					
A very serious problem					
A small problem	A small problem				
Not a problem					
Is it always the	same person that puts the baby to bed?				
	Yes				
	No				
If yes, who is it?	Mother				
	Father				
	Other person				
Does the baby r	move in his/her sleep?				
	Yes No				
The things that	disturb my baby's sleep are: (tick all that	apply)			
	Any sound, even very soft sounds				
	Radio or TV				
	People talking				
	Phone ringing				
	Other				
	Nothing disturbs my baby's sleep				
When my baby	wakes up he/she is usually:				
	Fussy				

	Crying	
	Hungry	
	Alert but quiet	
	Alert and active smiling when I approach	
	Other	
My baby can he	elp calm him/herself to sleep by:	
	Sucking on thumb or fingers	
	Holding a favourite blanket or soft toy	
	Sucking on a soother/dummy	
	Other	
When my baby needs help at night to calm down I:		
	Pick him/her up	
	Try talking and gently rubbing his/her back	
	Play music for him/her	
	Let him/her cry before I go in	
	Give him/her a soother/dummy or a bottle	
	Other	
I feel the best way to help my baby sleep through the night is to:		
	Stick to the same bedtime routine	
	Feed my baby shortly before putting him/her to bed	
	Let my baby cry him / herself to sleep	
	Comforting my baby whenever it's needed	
	Nothing I do seems to help	

Other		
Do you know what slee	ep training is?	
Yes No		
Have you tried sleep tr	raining?	
Yes, Th	ne Cry it Out approach	
Yes, Th	ne No Tears approach	
Yes, Fa	ading approach	
Yes, O	ther approaches	
No		
Will you be trying slee	p training?	
Yes, Th	ne Cry it Out approach	
Yes, Th	ne No Tears approach	
Yes, Fa	ading approach	
Yes, O	ther approaches	
No		
Did you attend a baby Yes No	massage course?	
IVO		
If yes, what age was yo	our baby when you starte	ed the course (weeks)
Did you use the massa Yes	ge as part of your daily ro	outine?
No		
Somet	imes	

If yes, what name and brand of product did you use when massaging your baby?
Screen –time
Does your child use a touch-screen device?
Never
Rarely (<1/week)
Occasionally (1-2 / week)
Regularly (3-5 / week)
Daily
If your child uses a touch-screen device Regularly or Daily, how long on average do they spend on
the device?
5-10 minutes
10-20 minutes
20-40 minutes
40-60 minutes
60-90 minutes
90-120 minutes
>120 minutes
What are your child's main activities when using the touch-screen device (Please tick all that apply)
Interacting with fun toddler games/puzzles
Interacting with educational game/puzzles
Watching TV shows/videos/ cartoons
Reading E books
Swiping photographs

Protocol/Sponsor Number: GB02/17UCC Principal Investigator: [name]

Baby's Health

Has your baby been unwell since or requ	ired any medical assistance since your last visit?
Yes	
No	
If Yes, why?	
Weight Loss/ Failure to thrive us	
Fever	
Reflux	
Colic	
Skin complaint	
Cough	
Ear/Eye problem	
Vesticoureteric reflux	
Pyloric Stenosis	
Meningitis	
Seizures	
Convulsions	
Infection	
Hernia	
Tongue tie	
Worried in general	
Other	
Did your baby require admittance to hos	pital?
Yes	
No	
If yes, how many times was he/she admi	tted

Protocol/Sponsor Number: GB02/17UCC Principal Investigator: [name]

Age when last admitted (weeks)

Has your baby received any vaccin	ations since your last visit?	
Yes	7	
No		
If yes, please provide details		
Туре	А	ge when received
in weeks		
6 month, 6 in 1(polio, diphtheria, who	ooping cough, tetanus, Hep B, H influenza B plus Men	C)
plus PCV & Men C		
12 month, MMR & Men B 13 month, Men C + Hib, plus PCV		
Other, please specify		
Mother's health		
Were you prescribed any medicati Yes	ion since your child was born?	
No No		
If YES, what were you prescribed?		
If YES, how long did you have to ta	wke it for?	
Days	inc 101;	
Weeks		

Protocol/Sponsor Number: GB02/17UCC Principal Investigator: [name]

Mother's Quality of Life

We would like for you t	o answer a few questions about your current health state.	
Please indicate which st	atements best describe your own health state today.	
Mobility	I have no problems in walking about I have some problems in walking about I am confined to bed	
Self- Care	I have no problems with self- care I have some problems washing or dressing myself I am unable to wash or dress myself	
Usual Activities E.g. Work, study, house	I have no problems with performing my usual activities I have some problems with performing my usual activities I am unable to perform my usual activities work, leisure or family activities	
L.g. Work, Study, House	work, leisure or failing activities	
Pain/Discomfort	I have no pain or discomfort I have moderate pain or discomfort I have extreme pain or discomfort	
Anxiety/Depression	I am not anxious or depressed I am moderately anxious or depressed I am extremely anxious or depressed	
In your own opinion, how good or bad is your own health today on a scale of 0-100 (Where 100 is the best imaginable

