[name], Prof of Paediatrics and Consultant Neonatologist, Cork University Maternity Hospital [name], Senior Lecturer and Consultant Pediatrician, Department of Pediatrics and Child Health and INFANT, UCC Cork University Hospital

Protocol/Sponsor Number: GB02/17UCC Principal Investigator: [name]

1 Background

It is well known that sleep is essential for brain development (3) and learning (4). Infants require extensive sleep for development of the hippocampus, pons, brainstem, and midbrain and for optimizing physical growth. It is also essential for *brain plasticity*; the genetically determined ability of the infant brain to change its structure and function in response to the environment. Studies in young animals have shown that sleep deprivation leads to increased programmed cell death, smaller brain size, and loss of brain plasticity, all of which have negative long-term impact on behaviour and learning ability (5-7).

Infant massage, a form of systematic tactile stimulation by human hands, improves sleep hygiene. Very little is known about how massage influences early brain development but it is certainly linked to the theory of environmental enrichment, which has been well established in animal models. (8-10).

2 Aims of the BabySMART project

The aim of this project is to optimise the infant's sensory experience through a multi-sensory enrichment programme, including massage (a massage utilising a scented lotion before sleep each day), to encourage more structured sleep and ultimately show improved developmental and cognitive outcomes.

3 Hypothesis

The BabySMART study will examine the effect of a structured sensory enrichment programme including massage, delivered by parents according to a structured programme following training, on both the quality and quantity of sleep and on subsequent neurodevelopment

4 Significance of the question

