6.1 Type of Trial

We will undertake a multi-centre, unblinded, randomised, controlled study to evaluate whether a multi-sensory enrichment programme in the first 4 months of life will improve sleep architecture and neurodevelopment in healthy infants.

We do not interpret this study as a clinical trial, as defined by the Control of Clinical Trials Act, 1987 and 1990.

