7.3 Sensory enrichment programme including infant massage

A total of 200 full term healthy infants will be recruited. Recruitment will take place at CUMH and UCL-ICH London. Parents will be invited to provide proxy consent for their infant to participate and also for their own participation in the BabySMART study.

Once Day 2 screening assessment is complete, parents will be informed that the next appointment will be in approximately 2 - 3 weeks and that a member of the BabySMART team will contact them to schedule this appointment. Randomisation will occur at this visit. Participants will be randomised to either a structured sensory enrichment programme including infant massage (intervention arm) or to the control arm.

The massage will be applied according to IAIM (International Association of Infant Massage). Created in 1976 by Vimala McClure, it is the first global organisation with a professional programme which is run in several countries around the world, due to its proven benefits. The purpose of IAIM is to create a nurturing touch and communication through training, education and research so that parents, caregivers and children are loved, valued and respected throughout the world community.

At the 2 week visit parents will be provided with training in infant massage by an instructor who has completed a Baby Massage Ireland trainer course. The massage should be carried out daily until the 4 month visit. Massage training will be completed on-site in the INFANT Research Centre in the new Paediatric unit in the CUH and the JOHNSON'S® HEAD-TO-TOE® extra moisturizing baby cream will be supplied at these appointments

Mothers will be informed about the enrichment programme which will include the benefits of baby massage, infant cues, duration of application, points of care for application and application technique at this stage. The technique of massage application will be shown to the mother by the researcher using a model baby (doll).

Mothers will be asked to apply the massage on their own baby as instructed and they will be observed to determine whether they applied the massage correctly or not. Training will be reinforced both at the training session and by the provision of a training DVD which will be provided to parents.

Baby massage education will also be given at drop in classes where a review of the strokes will be undertaken. Each parent's application of baby massage will be observed and evaluated for correct

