BabySMART Protocol Version 2.0 20 JUL 2017 Page 9

Protocol/Sponsor Number: GB02/17UCC Principal Investigator: [name]

technique. Extra JOHNSON'S® HEAD-TO-TOE® extra moisturizing baby cream will be supplied at these classes. Parents will be encouraged to massage their babies a minimum of 3 x 15-minute sessions including a minimum of 2 of the 6 areas to be massaged, every day for the first 4 months of life.

The researcher will follow HSE protocols to help women improve the care of their baby, or other questions that may arise; sleep positions, weaning, vaccines, feeding, bathing.

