Is your baby fed on a regular schedule eg. every 4 hours?
Yes, always
Yes, try to

No, fed on demand	
If giving solid foods, how old was he/sh	he when they first had solids?
Age (weeks)	
Have you given your baby any vitaming	s or supplements since your last visit?
Yes	
No	
If yes, please provide details	
Does your baby use a soother/dummy	?
Yes, regularly	
Yes, occasionally	
No	
Sleeping	
Sleeping Arrangements	
Infant cot in separate room	
Infant cot in parent's room	
In parent's bed	
Infant cot in room with sibling	
Other, please specify	
Sleeping Position	
On his / her belly	
On his / her side	
On his / her back	
Sleeping time during the day (between	າ 7am and 7pm)

Protocol/Sponsor Number: GB02/17UCC Principal Investigator: [name]

Hours

Sleeping time during the night (between 7pm and 7am) Hours
How long does it take to put your baby to sleep in the evening? Hours Minutes
Wakefulness time between 10pm and 6am Hours
How does your baby fall asleep?
While feeding
Being rocked
Being held
In bed alone
In bed near parent
When does your baby usually fall asleep at night (24 hour format)? Time
Do you consider your baby's sleep a problem?
A very serious problem
A small problem
Not a problem
Is it always the same person that puts the baby to bed?
Yes
No

If yes, who is it?	
Mother	
Father	
Other person	
Does the baby move in his/her sleep? Yes No	
The things that disturb my baby's sleep are: (tick a	ill that apply)
Any sound, even very soft sounds	
Radio or TV	
People talking	
Phone ringing	
Other	
Nothing disturbs my baby's sleep	
When my baby wakes up he/she is usually:	
Fussy	
Crying	
Hungry	
Alert but quiet	
Alert and active smiling when I app	proach
Other	
My baby can help calm him/herself to sleep by:	
Sucking on thumb or fingers	

	Holding a favourite blanket or soft	toy		
	Sucking on a soother/dummy			
	Other			
When my baby	needs help at night to calm down Pick him/her up	l:		
	Try talking and gently rubbing his/	her back		
	Play music for him/her			
	Let him/her cry before I go in			
	Give him/her a soother/dummy or	a bottle		
	Other			
I feel the best way to help my baby sleep through the night is to:				
	Stick to the same bedtime routine			
	Feed my baby shortly before putti	ng him/her	to bed	
	Let my baby cry him / herself to slo	еер		
	Comforting my baby whenever it's	needed		
	Nothing I do seems to help			
	Other			
Do you know w	hat sleep training is?			
	Yes			
Have you tried	sleep training?			
	Yes, The Cry it Out approach			

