	Yes, The No Tears approach			
	Yes, Fading approach			
	Yes, Other approaches			
	No			

Will you be tryi	ng sleep training?				
	Yes, The Cry it Out approach				
	Yes, The No Tears approach				
	Yes, Fading approach				
	Yes, Other approaches				
	No L				
If yes, what age	a baby massage course? Yes No was your when you started the course (weeks) massage as part of your daily routine? Yes No Sometimes				
If yes, what nar	ne and brand of product did you use when massaging your baby?				
Baby's Health Has your baby been unwell since or required any medical assistance since your last visit?					
Yes					
No					
If Yes, why?					
Weight Loss/ Fa	ailure to thrive us				
Fever					
Reflux					
Colic					

BABY SMART (Study of Massage the Protocol/Sponsor Number: GB02/1: Principal Investigator: [name] Irish Centre for Fetal and
Skin complaint		Neonatal Translational Resea
Cough		
Ear/Eye problem		
Vesticoureteric reflux		
Pyloric Stenosis		
Meningitis		
Seizures		
Convulsions		
Infection		
Hernia		
Tongue tie		
Worried in general		
Other		
Did you take your baby to the docto	or?	
Yes		
No		
If Yes, How many times?		
Did your baby need an antibiotic ?	٦	
Yes	_	
No		
If Yes, how many courses?		
Did your baby require admittance to	o hospital?	
Yes		
No		
If yes, how many times was he/she	admitted	

Age when last admitted (weeks)	
Since your last visit have you given your child pain re	lief medication?
Yes	
No	
If Yes, which medication? (please tick all that apply)	
Paracetamol eg. Calpol, Paralink	
Anti-inflammatories eg. neurofen, brufen Other, please specify Since your last visit have you given your child any	nat apply)
No	
Steroid cream	
Teething remedies (non-herbal)	
Colic Medication	
Reflux medication eg. baby gaviscon	
Antifungal creams	
Other, please specify	
Has your baby received any vaccinations since your I Yes No If yes, please provide details	ast visit?
Туре	Age when received
in weeks	
1. Tuberculosis (BCG)	
2. 2 month, 6 in 1 (polio, diphtheria, whooping cou	gh, tetanus, HepB, H influenza B plus Men C

3. 4 month, 6 in 1 (polio, diphtheria, whooping cough, tetanus, HepB, H influenza B plus Men C)

4. Other, please sp	ecify
Mother's health	
Were you prescribed an Yes No	ny medication since your child was born?
If YES, what were you p	rescribed?
If YES, how long did you Days Weeks	ı have to take it for?
For Mothers only - Mo	ther's Quality of Life
We would like for you t	o answer a few questions about your current health state.

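### The 4 month settling-time item gives no start point, so some intervention parents may count the pre-sleep massage itself as time taken to get the baby to sleep

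*Combined protocol and SAP*

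**What the plan says.** The sleeping part of the 4 month questionnaire (Appendix) asks "How long does it take to put your baby to sleep in the evening" and leaves hours and minutes to be filled in. Neither the item nor the rest of the protocol says when timing begins. The 18 month questionnaire repeats the item.

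Section 2 describes the massage as "a massage utilising a scented lotion before sleep each day". Section 7.3 gives the amount: "Parents will be encouraged to massage their babies a minimum of 3 x 15-minute sessions", every day. It also gives the duration: "The massage should be carried out daily until the 4 month visit". Infants are allocated to a "structured sensory enrichment programme including infant massage (intervention arm) or to the control arm". The control arm is not described further. Section 6.1 calls the trial a "multi-centre, unblinded, randomised, controlled study".

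The 4 month questionnaire also asks whether parents used "massage as part of your daily routine", answered yes, no or sometimes. No restriction to one arm is shown.

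**The concern.** The question can be read in two ways: from the start of the bedtime routine, or from the moment the parent tries to get the baby off to sleep. In most trials such vagueness adds noise to both arms alike. Here the assigned treatment can be part of the routine in one arm, and parents answer while they are still giving it. Those who take the first reading would report the treatment as part of the outcome.

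The error would run against the intervention: settling would look longer, and a real benefit could be masked or reversed. Recruiting more infants would not reduce it. It could not be corrected in analysis either. The form asks the clock time at which the baby falls asleep but not when settling starts, and the massage question records neither time of day nor length.

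**Working it through.** The documents state no figure for this item, so there is none to reproduce. They also give no SD, significance level, allocation ratio or dropout rate.

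**1. Does the massage overlap with the item?**

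| Element | Source | Status |
|---|---|---|
| No start point for settling time | Appendix, 4 month questionnaire | Documented |
| Massage comes before sleep, daily | Section 2 | Documented |
| 15 minutes per session, at least three a day | Section 7.3 | Documented |
| Continues until the 4 month visit | Section 7.3 | Documented |
| Assigned to one arm | Section 7.3 | Documented |
| A session precedes the evening sleep | None | Inferred; no time of day is fixed |
| Share of parents who count it | None | Unknown |

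**2. Size of the shift.** Let f be the fraction of intervention parents who massage before evening sleep and count one session. Assume the massage is added to the routine and replaces nothing, and that no control parent counts one.

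Shift = 15 × f minutes.

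- f = 25%: 15 × 0.25 = 3.75 minutes
- f = 50%: 15 × 0.50 = 7.5 minutes
- f = 100%: 15 minutes

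If a fraction g of control parents also massages and counts it, the shift becomes 15 × (f − g). With f = 50% and g = 25% it is 15 × 0.25 = 3.75 minutes.

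**3. Illustration against sampling error.** Assumptions: the planned 200 infants split 100 per arm, all retained; two-sided alpha 0.05; no true effect; SD of the item 15, 20 or 30 minutes. Mixed counting adds variance in the intervention arm:

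- SE = √[SD²/100 + (SD² + 15² × f(1 − f))/100]
- Probability of a significant difference = Φ(shift/SE − 1.96) + Φ(−shift/SE − 1.96)

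For SD 20 and f = 50%: SE = √[4 + (400 + 56.25)/100] = √8.5625 = 2.93; 7.5/2.93 = 2.56; Φ(0.60) ≈ 73%.

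| f | SD 15 | SD 20 | SD 30 |
|---|---|---|---|
| 25% | 39% | 25% | 14% |
| 50% | 91% | 73% | 41% |
| 100% | 100% | 100% | 94% |

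With 80 per arm the 50% row becomes 85%, 63% and 34%.

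The difference detectable with 80% power at 100 per arm is (1.96 + 0.84) × SD × √(2/100), which is 5.9, 7.9 and 11.9 minutes for the three SDs. A full 15-minute shift exceeds all three. A 7.5-minute shift exceeds only the first, and a 3.75-minute shift exceeds none.

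**The case against.** The strongest reply is that the link to the evening is inferred. Section 2 speaks of sleep, not evening sleep, and section 7.3 sets no time of day, so a family could give its sessions before naps. Control parents may massage on their own initiative, and they may count bathing, feeding or rocking. Massage may also replace some other part of the routine. **This stands.** It makes the bias a possibility and caps it at about 15 minutes times an unknown fraction.

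The item is also not a named endpoint, and no test on it is planned. The same questionnaire asks for day sleep, night sleep, night-time wakefulness and the clock time of falling asleep. Section 7.5 adds diary or app records of sleep, and section 7.2 a sleep EEG. **This stands too.** It limits the consequence to one measure. The other measures do not repair that measure, however: the EEG is timed to a daytime nap, and the diary or app is not said to record settling time.

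Finally, total bedtime effort, massage included, is a legitimate outcome, and subtracting one arm's soothing method while counting the other's could favour the intervention. **That is fair**, and the remedy has to allow both readings. It is no reason to leave the start point unstated.

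A reader might infer that the 18 month item is biased in the same way. It is not: the assigned massage ends at 4 months.

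**Conclusion.** The 4 month item is ambiguous in a way that can follow allocation. If intervention parents count a pre-sleep session, their mean settling time is lengthened by 15 minutes times the fraction who do: 3.75 minutes at 25%, 7.5 at 50%. This assumes an evening session, massage added to the routine, and no such counting among controls; each departure from these reduces the shift.

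A reader might go further and infer that the arms are known to differ on this item, that the trial faces a false-positive rate near 73%, or that the primary objective is compromised. The documents support none of these. How parents count is not recorded. The percentages rest wholly on an assumed SD, counting fraction, alpha and allocation, and fall to 14–39% at 25% counting. The primary objective covers infant sleep broadly and does not single out this item.

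What remains is a possible bias in one parent-reported sleep measure at one visit. It is worth correcting because the remedy is cheap, and because answers given without a start point cannot be put right later.

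**What to change.** In the 4 month questionnaire, for both arms:

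- **State one start point.** Count from when the parent begins settling the baby to sleep by any method (feeding, rocking, holding or laying down), after any massage has finished, until the baby is asleep. Including every ordinary settling method keeps the item defined for babies who fall asleep while feeding, which the form lists as an answer.
- **Add one line.** Was a massage given just before evening sleep, for how many minutes, and did the baby fall asleep during it?

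Settling time can then be analysed without the massage and, by adding the recorded minutes, with it. The analysis plan should say which of the two is the main version and how babies who fell asleep during the massage are handled. Use the same wording at 18 months for comparability only.

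The cost is two lines of wording in an appendix to the protocol, handled through the amendment process in section 12. The downside is that answers on the existing wording are not directly comparable with later ones and need a version flag.
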